1. To compare patient satisfaction and QOL between one-stage ADM and two-stage TE/I reconstruction without ADM following mastectomy. Patient satisfaction will be evaluated using the Breast Q© at two-weeks, as well as six months and one year following completion of reconstruction.

**Hypothesis:** Patient satisfaction and QOL will be higher in the ADM assisted one-stage implant reconstruction group compared to the two-stage TE/I group at all three time-points.

The **secondary objectives** of this study are:

1. To compare the short- and long-term complication rates between the two techniques.

**Hypothesis:** The use of ADM in one-stage prosthetic breast reconstruction is not associated with increased short- and long-term postoperative complications compared with the traditional two staged TE/I procedure.

2. To examine the overall aesthetic outcome achieved using the ADM facilitated one-staged breast reconstruction at six months and one year following completion of the reconstruction.

**Hypothesis:** The overall aesthetic outcome achieved using the ADM facilitated one-stage breast reconstruction is superior to that following the two-stage breast reconstruction.

3. To perform a cost-effectiveness analysis (CEA) of the two reconstruction methods using the net benefit regression model on person-level cost and effect data collected during the study.

**Hypothesis:** Both the direct and indirect cost will be reduced and patient-reported utility will be greater for the one-stage ADM method compared to the TE/I method.

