## **iia – 3. Preliminary Data**

Since our trial opened recruitment at University Health Network and Women's College Hospital, Toronto, Canada in September 2009, a total of 67 women have been registered into the trial. Fifty-one patients have been randomized to date, and the other 16 patients are still awaiting randomization. Randomization has been balanced between the one and two-stage procedure arms in blocks of eight and is stratified by study site as well as laterality of the reconstruction. Breakdown of patients randomized by site and laterality is outlined below:

University Health Network (N=33)	Unilateral	Bilateral
1 stage w/ AlloDerm/ Implant (N=17)	(n=7)	(n=10)
2 stage w/ TE (N=16)	(n=8)	(n=8)

Women's College Hospital (N+18)	Unilateral	Bilateral
1 stage w/ AlloDerm/ Implant (N=10)	(n=2)	(n=8)
2 stage w/ TE (N=8)	(n=2)	(n=6)

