#### Interim analysis of complication rates

An interim analysis of short-term complications revealed similar rates of postoperative complications between the two arms of the trial. In the one-stage AlloDerm assisted implant study arm, the rate of major complications is 0 and the rate of minor complications is 7%. There has been 1 case of cellulitis and 1 case of infected seroma both successfully treated with antibiotics. In the two-stage TE/I control arm, the rate of major complications is 4% and the rate of minor complications is 12.5%. In this arm, there were 2 cases of cellulitis successfully treated with antibiotics, 1 case of incisional dehiscence managed with conservative dressing changes, and 1 case of infected seroma that resulted in premature removal of the expander.

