#### Study Schema:

Baseline Measure	Skin-sparing or Nipple-sparing mastectomy	Outcome Measure
Stratify by:		
1. Site	Acellular dermal matrix assisted one-stage implant reconstruction	1. Breast Q ©
UHN WCH VGH		2. EQ-5D
2. Laterality		3. Complications
Unilateral Bilateral		4. Aesthetics
	Two-stage tissue expander/implant reconstruction	5. Cost-effectiveness

The **primary outcome** evaluated will be **patient-reported satisfaction and quality of life** associated with the use of ADM in one-stage immediate prosthetic breast reconstruction following skin-sparing or nipple-sparing mastectomy. Patient-reported satisfaction and quality of life will be measured using the Breast Q© questionnaire. These questionnaires will be administered to patients prior to mastectomy, at two weeks following the mastectomy and immediate reconstruction, 6 months and one year (+/- 1 month) following completion of reconstruction. It is hypothesized that ADM assisted one-stage prosthetic breast reconstruction will be associated with improvement in patient-reported satisfaction and quality of life compared to the conventional two-stage TE/implant reconstruction.

The **secondary outcomes** will include **short and long-term complication rates**, overall **aesthetic outcome** including capsular contracture formation at six month and one-year following completion of the reconstruction, and a **cost effectiveness analysis (CEA)**. For the cost-effectiveness analysis, person-level cost and effect data will be collected throughout the study. The cost data will come from hospital cost accounting systems and patient reports. The patient outcome data will be collected at months 6 and 12 months post-mastectomy by the Breast Q© and EQ-5D. The primary measure of effectiveness will be the global Breast Q© score and the secondary measure will be quality adjusted life years (QALY) as measured by the EQ-5D. It is hypothesized that the short- and long-term complication rates will be comparable between the two study arms, while the overall aesthetic outcome will be superior with less severe capsular contracture in the ADM assisted one-stage than the two-stage TE/implant reconstruction. Lastly, we hypothesize ADM assisted one-stage implant reconstruction will be the more cost effectiveness method of implant reconstruction following mastectomy than the standard two-stage TE/I method.

Timing of Questionnaires

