#### **iib-7. Confounders and their Measurements**

Critical covariates will be identified at baseline and documented in the demographic assessment forms. These confounders can be conceptually divided into procedure specific, patient specific, and disease specific confounders. Analysis will be adjusted for the confounders using both stratification and multivariate regression. (see section on Outcome and their measurements) Stratified randomization is

performed based on laterality of the reconstruction (unilateral vs. bilateral) and study site. Other procedure specific confounders include skin-sparing vs. nipple-sparing mastectomy and the primary reconstructive surgeon. The patient specific confounders will include age, body mass index; socioeconomic status assessed using proxy measures of income and highest obtained level of education and marital status. Co-morbidities will be categorized as having one or more the following possible chronic conditions (emphysema, heart disease, diabetes, hypertension, stroke, arthritis, or other chronic condition). The disease specific confounders will include stage of breast cancer and present or past chemotherapy treatment.

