### **9c. Measurement of the Primary Objective:**

#### ***i) Primary Analysis***

Each of the two domain-specific summary scores on function and satisfaction will be transformed on a scale from 0 to 100 using RUMM software. Mean scores and standard deviation for each surgery group will be calculated and compared. To address our primary aim of comparing patient satisfaction and quality of life between **Group 1** (one-stage with ADM) and **Group 2** (two-stage group without ADM) before and at the three post mastectomy follow up reference time points, we will use the **repeated measure analysis** to examine the time effect and time-group interaction. In all analyses, statistical significance will be designated at  $p <= 0.05$  level.

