#### ***ii) Secondary Analysis***

Short-term (intra-operative and early post-operative) and long-term postoperative complications will be documented and collected prospectively at each site by the study coordinator. Group comparisons will be performed using the Pearson's chi-square test or binomial test, where appropriate for these categorical variables. Repeated measure analysis will be used for Breast Aesthetic Score at 6 and 12 months post mastectomy. The Modified Baker Scale for capsular contracture results in an ordinal variable which will be compared using the Pearson's chi-square test.

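### Complications are hypothesised as no worse with ADM, but the plan offers only a test of difference, with no effect estimate or interval, and a non-significant result cannot support that hypothesis

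*Combined protocol and SAP*

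**What the plan says.** Under Specific Aims, the hypothesis for secondary objective 1 is that ADM in one-stage reconstruction "is not associated with increased short- and long-term postoperative complications compared with the traditional two staged TE/I procedure". The text below the Study Schema repeats it: "short- and long-term complication rates will be comparable between the two study arms".

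The analysis is in 9c ii) Secondary Analysis, where the arms are compared by Pearson's "chi-square test or binomial test, where appropriate for these categorical variables". The criterion comes from 9c i) Primary Analysis: "In all analyses, statistical significance will be designated at" p ≤ 0.05. Neither section names an effect measure or interval for complications, or says how a non-significant result will be read.

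On adjustment, iib-7 says "Analysis will be adjusted for the confounders using both stratification and multivariate regression". Section 9a repeats this, mentioning stratification and control within the repeated measures analysis.

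The Preliminary Data section states "An interim analysis of short-term complications revealed similar rates of postoperative complications between the two arms of the trial". For the two-stage arm, "the rate of major complications is 4% and the rate of minor complications is 12.5" (per cent); for the one-stage arm the figures are 0 and 7%. No interval accompanies them.

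**The concern.** The hypothesis says that something is absent: an increase in complications. The test takes equality as its null and can only produce evidence against it. If the arms really are alike, the usual outcome is p > 0.05, and too few patients produce the same outcome. The p-value alone cannot separate the two.

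This is a safety question of some weight. The Significance section attributes the preference for two-stage reconstruction to high complication rates with traditional one-stage implants. A conclusion that ADM avoids this would need an upper bound on the excess risk, and the plan does not ask for one.

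**Working it through.** **Inputs.** 72 per arm (iib-10 Sample Size). Significance level 0.05 (9c i). Sidedness is not stated; I take two-sided. Interim denominators are the sums of the randomized patients by site in iia-3: ADM 17 + 10 = 27 and TE/I 16 + 8 = 24, together 51 ("Fifty-one patients have been randomized to date"). These reproduce the interim rates: 2/27 = 7.4%, 3/24 = 12.5%, 1/24 = 4.2%. If all four control-arm events were in different patients, the any-complication rate is 4/24 = 16.7%. The 10% rate and all sizes of rise are my assumptions. The documents give no planning rate for complications and no long-term rate.

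**The plan's own figure.** The trial is sized on Breast Q: difference 10, SD 20, power 85%. n per arm = 2(z₀.₉₇₅ + z₀.₈₅)² × SD²/difference² = 2 × (1.960 + 1.036)² × 400/100 = 71.8, so 72. This reproduces and supports a two-sided reading. No such calculation exists for complications.

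**Chance that the planned test misses a true rise.** For counts i (TE/I) and j (ADM) out of n = 72, the uncorrected statistic is X² = 2n[i(n−j) − j(n−i)]² / [n²(i+j)(2n−i−j)]. I summed the binomial probabilities of all pairs with p > 0.05.

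| TE/I rate | Source | Misses a doubling | Misses +10 points |
|---|---|---|---|
| 4.2% | interim major, 1/24 | 82% | 42% |
| 10% | assumed | 61% | 61% |
| 12.5% | interim minor, 3/24 | 50% | 64% |
| 16.7% | 4/24, if different patients | 35% | 69% |

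With equal rates the test is non-significant about 95% of the time in every row. So p > 0.05 is expected if the hypothesis is true and is also common if it is false.

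**One possible result.** With 9/72 (TE/I) versus 18/72 (ADM), X² = 3.69 and p = 0.055; the difference is +12.5 points, Newcombe 95% CI −0.3 to +25.0. This example is borderline: 9 versus 19 gives p = 0.035, and 12 versus 24 gives p = 0.021.

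**The interim data.** The Newcombe interval combines the Wilson limits (l, u) of each arm: lower = d − √[(p₁−l₁)² + (u₂−p₂)²], upper = d + √[(u₁−p₁)² + (p₂−l₂)²].
- ADM 2/27: p₁ = 0.074, limits 0.021 to 0.234.
- TE/I 4/24: p₂ = 0.167, limits 0.067 to 0.359.
- d = −0.093; lower = −0.093 − 0.199 = −0.292; upper = −0.093 + 0.188 = +0.096.

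That is −9 points (−29 to +10). Minor complications only, 2/27 versus 3/24: −5 points (−24 to +13).

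**Precision at the end of the trial.** With equal rates p, the 95% half-width is about 1.96√[2p(1−p)/72]: 9.8 points at 10%, 10.8 at 12.5%, 12.2 at 16.7%, and 6.5 at 4.2%.

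**The case against.** Complications are secondary and the trial is sized on Breast Q, so limited power is not a design error. That stands. A reader might infer from the table that the trial is too small, or that it misses a doubling about half the time. The documents do not support that as a general statement: 12.5% is an interim minor-complication rate, the doubling is assumed, and at 16.7%, which is closer to an any-complication endpoint, the figure is 35%.

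The plan nowhere says that p > 0.05 will be read as no increase. That also stands: the misreading is left open, not prescribed. The interim paragraph shows how easily it could happen, but it is a descriptive passage in a funding narrative and its point estimate favours ADM. It should not be read as a sign of harm.

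If counts by arm are published, a reader can compute the interval, as I did, so the information is not lost. A significant difference in favour of ADM would also support the hypothesis. What remains is that comparability, the result the sponsor predicts, has no planned analysis able to support it.

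Finally, the adjustment wording in iib-7 and 9a might be taken to cover complications, or to exclude them because 9a mentions repeated measures and the Stratification section describes the randomization. Either reading can be argued. On neither does the text specify an effect estimate or interval for complications.

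**Conclusion.** The mismatch holds. The hypothesis is one of no increase, the only specified analysis is a test of difference, and a non-significant result from it cannot support the hypothesis. This does not depend on any assumed rate.

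The miss rates (35–82% for a doubling, 42–69% for a 10-point rise) show why an interval is needed. They rest on 72 evaluable patients per arm, a two-sided uncorrected chi-square test, short-term interim rates from 51 patients, and rises that I chose. The interim interval of −29 to +10 points also assumes that the four control-arm events were in four patients and that all 51 randomized patients were assessed.

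The point concerns inference on a secondary endpoint. It is worth correcting and leaves the primary analysis untouched.

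**What to change.** In 9c ii) Secondary Analysis:

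1. Make the main complication result the risk difference (ADM minus TE/I) in the proportion of patients with at least one complication, with a two-sided 95% CI, separately for short-term and long-term complications.
2. Preferably stratify by the randomization factors, site and laterality (for example a Mantel-Haenszel risk difference), with a rule fixed in advance for pooling sparse strata. The unilateral stratum at Women's College Hospital so far holds 2 versus 2 patients.
3. State that p > 0.05 will not be read as no increase.
4. Choose one of two routes. Either fix and justify a margin before the final analysis, disclosing that interim rates by arm were already known, or state that the comparison is estimative and reword the hypothesis to match. Without one of these, the upper limit has nothing to be judged against.

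The cost is SAP wording and a little analysis work, with no new patients or data. The downside is a wide interval, with a half-width of about 10–12 points at two-stage rates of 10–16.7%, so the result may be inconclusive. For illustrative margins m and truly equal rates, the chance that the upper limit falls below m is about Φ(m/SE − 1.96), with SE = √[2p(1−p)/72]. For 10 points it is 44% at a rate of 12.5% and 36% at 16.7%; for 15 points it is 78% and 68%.

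A separate, minor improvement: 9c ii) itself describes the Baker grade as ordinal, and the Study Schema text predicts milder contracture with ADM. Pearson's chi-square is valid but ignores order. A rank test or proportional-odds model would use it, with one grade per patient at one time point named in advance, since grading occurs at both six months and one year.

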2. **long-term aesthetic result**: Evaluation of the overall aesthetic result and capsular contracture grade will be performed at six months and one year following the completion of reconstruction. A routine physical examination will be performed by the attending surgeon and photographic documentation (5 standardized photographs) of the reconstruction will be obtained at the six month and one-year follow-up visit. A panel of three independent, blinded observers will subsequently evaluate the overall aesthetic result using the three-point, five item, Breast Aesthetic Score described by Lowery with the use of photographic documentation. Capsular contracture will be graded by the examining physician and will be graded using the Modified Baker Scale for Reconstructed Breasts, which is widely accepted to be the gold-standard measure of capsular contracture grade.
3. **cost-effectiveness**: Costs and effects will be simultaneously analyzed by collecting person-level cost and effect data. The cost data will come from hospital cost accounting systems and patient reports. The patient outcome data will be collected at months 6 and 12 months post-mastectomy by Breast Q $\circ$

and EQ-5D. The frequently used generic HRQoL instrument EQ-5D will be piggy-backed to the Breast QoL at the 2 post-mastectomy time-points to generate a utility value for current health. The primary measure of effectiveness will be the Breast Q score and the secondary measure will be quality adjusted life years (QALY) as measured by the EQ-5D (APPENDIX 6)

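### Capsular contracture is called ordinal but tested with an unordered Pearson chi-square, and the plan does not say how a bilateral woman's two grades enter the test

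*Combined protocol and SAP*

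**What the plan says.** All references are to the combined protocol and SAP.

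- **Test.** Section 9c ii: "The Modified Baker Scale for capsular contracture results in an ordinal variable which will be compared using the" Pearson chi-square test. No trend test, ordinal model or score is mentioned.
- **Measurement.** Section iib-8, item 2: "Capsular contracture will be graded by the examining physician", and the grade "will be graded using the Modified Baker Scale for Reconstructed Breasts". The name of the scale points to the breast as the thing graded, but the section does not say so outright.
- **Hypothesis.** Section iib-1, in the text after the Study Schema, expects contracture to be milder in the one-stage arm. That is a statement about direction along the grade order.
- **Randomization.** Women are randomized. Section iia-3 says allocation is "stratified by study site as well as laterality of the reconstruction", and its table shows that bilateral reconstruction was the more common case.
- **Unit of analysis.** Nothing in 9c ii says whether women or breasts are counted for contracture, or how two grades from one woman are combined.
- **Significance level.** Section 9c i: "In all analyses, statistical significance will be designated at" the 0.05 level, in all analyses.

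**The concern.** There are two separate matters.

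The first does not depend on the unit of analysis. Pearson's chi-square asks whether the two arms differ in any way across the grade categories. Shuffling the grade labels leaves the statistic unchanged. The plan's hypothesis is about severity, so the test spreads its power over patterns that nobody has hypothesised. A significant result would also not by itself show that one arm had milder contracture.

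The second is an open choice. A bilateral woman can contribute two grades, which are likely to be correlated because they share one patient and one allocation. The chi-square test needs independent observations. If each woman contributes one result, that condition is met. If all breasts are pooled, it is not met, and the test rejects too often under the null. With most randomized women bilateral, the choice matters, and as written it could be made after the data are seen.

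**Working it through.** **Plan's own figures.** The plan gives no power or error calculation for contracture. Its 72 per arm is for the Breast Q (difference 10, SD 20, two-sided 5%, power 85%) and reproduces: 2 × (1.960 + 1.036)² × 20² / 10² ≈ 71.8, rounded up to 72. It says nothing about power for contracture.

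**1. Cost of ignoring the order.** Suppose the effect lies wholly along the ordering and a 1-df ordinal test has 80% power. The 80% is a reference point, not a plan figure.

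- Noncentrality: λ = (1.960 + 0.842)² = 7.85.
- Power on k df: P(noncentral χ² with k df and noncentrality λ > 5% critical value for k df).
- The documents do not give the number of grades, so two cases are shown.

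| Test | df | Critical value | Power |
|---|---|---|---|
| Ordinal | 1 | 3.841 | 80% |
| Pearson, three grades observed | 2 | 5.991 | 71% |
| Pearson, four grades observed | 3 | 7.815 | 64% |

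**2. Women and breasts (table in iia-3).**

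- Unilateral: 7 + 8 + 2 + 2 = 19.
- Bilateral: 10 + 8 + 8 + 6 = 32.
- Bilateral share: 32/51 = 62.7%.
- Breasts: 19 + 2 × 32 = 83.

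**3. Error rate if breasts were pooled as independent.** With m breasts per woman, the design effect is DE = 1 + (Σm²/Σm − 1) × ICC.

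- Σm² = 19 + 4 × 32 = 147 and Σm = 83, so DE = 1 + 0.771 × ICC.
- For a 1-df test, true error = 2 × [1 − Φ(1.96/√DE)].
- The left-right ICC is not in the documents. It is an assumption, shown over its full range.

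| ICC | DE | True error of a nominal 5% test |
|---|---|---|
| 0 | 1.00 | 5.0% |
| 0.3 | 1.23 | 7.7% |
| 0.5 | 1.39 | 9.6% |
| 0.7 | 1.54 | 11.4% |
| 1 | 1.77 | 14.1% |

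**4. Sensitivity.**

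- *Laterality mix.* At 50% bilateral, Σm²/Σm = 2.5/1.5 = 1.667. ICCs of 0.3, 0.5 and 0.7 then give 7.4%, 9.0% and 10.6%.
- *Several grades.* The 1-df formula describes a two-category grade. A simulation with four ordinal grades (45 bilateral and 27 unilateral women per arm, 20,000 runs) gave about 7.4% at ICC 0.33, 9.1% at 0.49 and 13.2% to 13.6% at 0.71.

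**5. What the investigators have counted so far.** From iia-3, the one-stage arm had 27 women (9 unilateral, 18 bilateral, 45 breasts). The two-stage arm had 24 women (10 unilateral, 14 bilateral, 38 breasts).

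| Interim complication rate | Reported | Events / women | Events / breasts |
|---|---|---|---|
| One-stage, minor | 7% | 2/27 = 7.4% | 2/45 = 4.4% |
| Two-stage, major | 4% | 1/24 = 4.2% | 1/38 = 2.6% |
| Two-stage, minor | 12.5% | 3/24 = 12.5% | 3/38 = 7.9% |

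Only the women denominator matches the reported rates.

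**The case against.** The strongest reply is that a gap in wording is being read as a planned error. A reader might infer from 9c ii that the trial will count breasts as independent and so run contracture at an 8% to 11% error rate. The documents do not support that. The section names no unit, and the patient is the unit in the enrolment target (iib-1), the intention-to-treat rule (9b) and the sample size (iib-10). If one result per woman is used, there is no inflation. The percentages also need an assumed ICC and a two-category grade, and the bilateral share comes from 51 women at two sites, before the third site contributed. All of this stands, and the error rates are illustrations only.

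A reader might also extend the point to complications, because the same section says "Group comparisons will be performed using the" Pearson chi-square or a binomial test for them. That does not hold either: the interim complication rates were divided by women.

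On ordering, the reply is that Pearson's chi-square on ordinal data remains valid and only loses power, on a secondary outcome. That is correct. The loss shown is also the case most favourable to an ordinal test. If arms differed in a way that did not follow the order, such as more grades at both extremes, Pearson could do better. But the plan's hypothesis concerns severity, so the ordered alternative is the relevant one.

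Finally, sections iib-7 and 9a already promise adjustment by stratification. That is a general statement. Section 9c ii names no stratified test for contracture, and stratification does not deal with two grades from one woman.

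**Conclusion.** The point holds as a mismatch between variable and test, with an unstated rule for bilateral women attached. The mismatch follows from the plan's own words. Its cost is roughly 9 to 16 points of power (80% down to 71% or 64%), assuming an effect along the grade order, a reference power of 80% and three or four grades observed. It applies whichever unit is counted.

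The unit-of-analysis part is missing detail, not a demonstrated error. Its consequence runs from none (women counted) to the inflation tabulated above (breasts pooled), depending on the unknown correlation, the number of grade categories and the final laterality mix. No defect is claimed for complications, and the primary Breast Q analysis is not affected. The point ranks as a cheap improvement.

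**What to change.** In 9c ii, replace Pearson's chi-square for the Baker grade with an ordinal test at woman level. Take the worst breast per woman and compare arms with a Cochran-Mantel-Haenszel row-mean-score test stratified by site and laterality. These are already the randomization strata. Stratifying by laterality also matters because the worse of two breasts will tend to grade higher than a single breast. If both breasts are to be used, specify a proportional-odds model fitted by GEE with clustering on woman. Choose one before the contracture data are compared by arm.

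The cost is a sentence or two of SAP text and slightly more analysis work. No new patients or data are needed. The worst-breast rule discards the better breast's grade; the GEE option keeps it at the price of a more complex model. Either option removes the risk of counting a bilateral woman twice.
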